**Research Question(s):**

Primary: Does lidocaine versus saline as a steroid diluent affect objective upper extremity strength following cervical epidural steroid injection in patients being treated for cervical radicular pain?

Secondary: Does lidocaine versus saline as a steroid diluent affect short-term pain, function, medication use, and global impression of change outcomes of cervical epidural injection for the treatment of radicular pain?

**Null Hypothesis:**

1. Cervical epidural steroid injections that include local anesthetic as a diluent have no effect on objective upper extremity strength following the injection.
2. Cervical epidural steroid injections for radicular pain that include lidocaine compared to saline as a diluent do not improve short-term pain, function, medication use, and global impression of change outcomes.

**Introduction**

Cervical radicular pain is a common problem that is often treated by epidural steroid injection (1). While clinical practice guidelines do not specifically recommend or discourage the use of local anesthetic in the epidural injectate (2), the majority of the published literature on clinical outcomes of cervical epidural steroid injection includes the use of lidocaine in the epidural injectate (3-11). Consequently, many practitioners elect to use local anesthetic in the epidural injectate in order to obtain additional diagnostic information when the precise source of pain is not clear from clinical presentation and imaging. Local anesthetic may also be included in order to provide immediate pain relief in cases of painful acute radicular symptoms.

Local anesthetic injection into the epidural space has the potential to cause transient weakness of the upper extremities. High dose local anesthetic in the cervical epidural space (12) and inappropriately placed low-dose local anesthetic in the subdural space or subarachnoid space (13, 14) are known to cause motor weakness. Appropriately placed, low-dose local anesthetic injected into the epidural space via a transforaminal approach, in close proximity to the exiting spinal nerve root, causes motor block in a small proportion of patients (15). However, the effect of low-dose injection of local anesthetic in the cervical interlaminar epidural space on objective upper extremity strength has not been characterized in the published literature. This proposition affects post-procedure instructions, as even mild weakness may pose a hazard during performance manual activities that require the upper extremity/extremities such as using a handrail or cane handle for support.

Dynamometry is an established and validated method for assessing muscle strength and motor neuron function with high reliability, and has been used to objectively assess changes in upper extremity strength.

This study aims to determine whether a standard dose of 2 mL 1% lidocaine included as a steroid diluent in a C7-T1 cervical interlaminar epidural steroid injection (CESI) causes an objective change in strength as measured by dynamometry. We hypothesized that cervical epidural lidocaine will cause an objective decrease in strength in functional movements of the upper extremity.

### **Significance:**

Cervical radicular pain is relatively common, often treated with epidural steroid injection (ESI), when conservative treatments like oral analgesics, physical therapy, and activity modification have failed. There are no universal clinical practice guidelines for the use of diluents when CESI are performed.

Interlaminar CESI may be performed with or without the use of local anesthetics, due to training bias or theoretical concerns of weakness. CESI without the benefit of local anesthetic as a steroid diluent increases the latency of pain relief and may decrease diagnostic information immediately after a CESI with regard to pain generators responsible for symptoms, and may potentially decrease patient satisfaction.

By evaluating the effects of local anesthetic as a diluent during interlaminar cervical ESI, we will enhance the safety of this treatment with regard to expectations of objective motor weakness as well as post procedure pain control in the recovery phase after the injection procedure.

Additionally, investigation of short-term pain, function, medication use, and global impression of change following use of local anesthetic versus saline as a diluent during interlaminar cervical ESI will provide evidence to inform the optimization of clinical outcomes related to steroid diluent choice.

### **Subjects**

A total of 104 subjects, aged 18-80 on the day of enrollment, will be recruited for participation in this study. Patients will be randomized to one of two groups based on a random computer-generated schedule.

Those assigned to Group #1 will undergo a interlaminar cervical ESI with local anesthetic as a steroid diluent. Those in Group #2 will receive a interlaminar cervical ESI with saline as a steroid diluent.

### **De-identification**

All subjects will be assigned a unique alphanumeric identifier. No personally identifiable information will be used in the final database, in order to ensure compliance with HIPPA and hospital policy. All data will be stored on a highly secure, password protected computer.

## **Participant Recruitment**

Our intended subject demographic includes an active population between the ages of 18 and 80 years on the day of enrollment. We intend to recruit participants primarily through word-of-mouth and from a database or participant pool for which participants have given prior permission to be contacted for research studies. Additionally, recruiting will take place through the distribution of flyers to the Health Sciences Education Building, University of Utah Student Life Center, the University of Utah South Jordan Health Center, the University of Utah Orthopaedic Center, and the University of Utah hospital. Upon first contact with the potential participant, the study coordinator or research associate will provide a basic description of the study and review inclusion and exclusion criteria, general health status, and past and current athletic participation. Interested volunteers who qualify will be asked to report to the University of Utah Orthopaedic Center. Prior to screening procedures and after being informed of any potential risks involved in the study, volunteers will be asked to provide written, informed consent for study participation.

Inclusion criteria:

- 1) Age 18-80.
- 2) Clinical diagnosis of cervical radicular pain.
- 3) Magnetic resonance imaging pathology consistent with clinical symptoms/signs.
- 4) Numerical Rating Scale (NRS) pain score of 4 or higher.
- 5) Pain duration of more than 6 weeks despite trial of conservative therapy (medications, physical therapy, or chiropractic care).
- 6) Patients who will undergo CESI for treatment of cervical radiculitis.

Exclusion criteria:

- 1) Refusal to participate, provide consent, or provide communication and follow-up information for duration of the study.
- 2) Inability to perform handgrip or arm strength testing.
- 3) Contraindications to Cervical ESI (active infection, bleeding disorders, current anticoagulant or antiplatelet medication use, allergy to medications used for CIESI, and pregnancy).
- 4) Cervical spinal cord lesions; cerebrovascular, demyelinating, or other neuro-muscular muscular disease.
- 5) Patient request for or requirement of conscious sedation for the injection procedure.

**Study design:**

**Prospective, randomized, controlled, double blinded trial in patients undergoing CESI for symptoms of cervical radicular pain.**

Patients will be randomized to group #1 or #2 based on a random computer-generated schedule.

Group #1: Interlaminar cervical ESI at the C7-T1 level with triamcinolone 80 mg (40 mg/mL) + 2 mL 1% lidocaine (total volume 4 mL).

PI: [name]

Title: Do Cervical Interlaminar Epidural Steroid Injections with Low-dose Lidocaine Cause Transient Objective Upper Extremity Weakness? A

Prospective Randomized Controlled Trial

Version: 3.0, 17JUL2017

Group #2: Interlaminar cervical ESI at the C7-T1 level with triamcinolone 80 mg (40 mg/mL) + 2 mL preservative saline (total volume 4 mL).

Adults who are eligible and scheduled to have an epidural steroid injection with triamcinolone for treatment of cervical radicular pain at the University of Utah Orthopaedic Center or University of Utah South Jordan Health Center will be approached by authorized research personnel. All eligible patients will be offered to participate in the study and all patients will sign a written informed consent form before proceeding and will also be consented for the procedure. Participating in the study is voluntary. The patients may choose not to enroll in the research. Patients will be presented with the same options of treatment whether they enroll or decide not to.

### **Power Analysis**

Statistical Plan & Sample Size Calculation:

Size of study groups:

Group 1: n = 52

Group 2: n = 52

A power analysis was performed based upon previous observations of UE strength (28) using Fisher's Exact Test. Sample sizes of 52 in each of the two treatment groups will achieve > 80% power to detect a group different in proportions, assuming 20% of patients in the Lidocaine group will demonstrate a motor deficit after the CESI and those in the Saline group will demonstrate no difference in motor strength after the CESI, assuming a 2% measurement error with the strength testing method described. The alpha level of this test statistic is set at 0.05, but the significance level actually achieved by this study design is 0.0004.

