### **Procedure**

All patients evaluated in the University of Utah Orthopaedic Center who will have a CESI with triamcinolone will be considered for participation in the study. Subjects will be consented for participation in the study and informed consent will be obtained. Each subject will be randomized into a group assignment in a 1:1 manner, #1 or #2, as outlined in the Methods section above. All documentation will be stored using a unique coded identifier to ensure compliance with HIPPA.

A Report Form will be used to record all pre- and post-procedure data (See Appendix)

In every participant in Control Cohort, Group 1 and Group 2, a pre-procedure NRS pain score, pain medication use, and presence of subjective or objective symptoms of UE weakness will be recorded. Bilateral handgrip, wrist extension, elbow flexion, and elbow extension strength (myotomes C5-T1) will be measured by a trained research assistant prior to the injection procedure using a handheld JAMAR® PLUS+ digital dynamometer (Sammons Preston, Bollingbrook, IL) for hand grip strength and a Lafayette Manual Muscle Testing System model 01163 (Lafayette Instrument Company, Lafayette, IN) for arm strength assessment. Three baseline strength measurements will be recorded for each strength test (20,21). Validation studies using similar protocols for upper extremity functional strength measurement show a high degree

of test-retest reliability with a narrow range of variability [22–26]. Additionally, light touch and pinprick sensory testing in the C5-T1 dermatomes will be performed with a tapered whisp of cotton and a disposable safety pin, respectively, in accordance with the methods described when performing an American Spinal Injury Association (ASIA) examination in accordance with the international standards for neurological classification of spinal cord injury (27).

Measurements will be taken prior to and 30 minutes following the injection procedure. Participants in Group #1 and Group #2 will also be queried with the Upper Extremity Functional Index (UEFI) before the injection procedure and again 1 day after the procedure (administered via telephone).

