### **Data Collection:**

#### **1 Data evaluation (See Case report form)**

#### **2 Interpretation of Anticipated Results:**

### **Statistical analysis**

Differences in strength as measured by dynamometry pre-and post-injection will be assessed by Fishers exact test.

Means and standard deviations of subject demographic data, as well as pain scores and UEFI scores will be calculated.

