### **Data Analysis Plan**

The primary outcome will be the proportion of participants with 50% or greater reduction in neck and arm pain on the NRS pain score at the 1-month follow-up assessment. Secondary outcomes included reduction in median NRS pain score (both neck pain and arm pain), NDI-5, MQS III, opioid consumption in daily morphine equivalents, PGIC score, and satisfaction score. Secondary outcomes will also be defined based on categorical “responder analysis” definitions of important clinical change given the National Institutes of Health recommendation for responder analysis in the assessment of therapeutic spine pain interventions. The responder analysis will include the proportion of patients with 30% or greater improvement on the NDI-5, a PGIC score less than 3 (indicating “improved” or “very much improved”), a 6.8 or greater point reduction on the MQS III score (equivalent to approximately 10 daily morphine equivalents), and the proportion of participants who undergo surgical spine surgery.

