### **Primary outcome:**

- Change in strength for each individual in each treatment group before and 30 minutes after CESI
- Categorical analysis based on a minimally clinically important change of 19.5% for upper extremity strength assessment (29).

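### Cheap improvement, not an error: Boschloo's exact test would give the motor-deficit comparison about 87% power where Fisher's gives 80%, with type I error still at most 0.05

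*Combined protocol and SAP*

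**What the plan says.** The Power Analysis section uses Fisher's exact test with 20% of lidocaine patients showing a motor deficit. Saline patients are taken to show no change, "assuming a 2% measurement error with the strength testing method described". It concludes: "Sample sizes of 52 in each of the two treatment groups will achieve > 80% power to detect a group different in proportions". On the significance level it adds: "The alpha level of this test statistic is set at 0.05, but the significance level actually achieved by this study design is 0.0004".

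The Statistical analysis section plans the same test: "Differences in strength as measured by dynamometry pre-and post-injection will be assessed by Fishers exact test". Under Primary outcome, the cut-off for the binary result is given as "Categorical analysis based on a minimally clinically important change of 19.5% for upper extremity strength assessment".

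The Procedure section says of allocation: "Each subject will be randomized into a group assignment in a 1:1 manner". It does not mention blocking. On measurement it says: "Bilateral handgrip, wrist extension, elbow flexion, and elbow extension strength (myotomes C5-T1) will be measured by a trained research assistant". No unconditional exact test is mentioned, and neither the sidedness of the test nor an expected loss rate is given.

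**The concern.** Fisher's test conditions on the total number of events. When events are few it uses much less than its nominal 0.05, and the plan's own 0.0004 shows this. The unused error is power given up. Power sits only just above the 80% target, so losing one patient from each arm already takes it below.

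The primary research question is whether lidocaine affects strength. At the plan's assumptions and 52 evaluable patients per arm, the choice of test sets the chance of missing a true 20% v 2% difference at 19.7% (1 − 0.803) or 12.5% (1 − 0.875).

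A smaller point is wording. A reader could take 0.0004 as the trial's false-positive risk. It is the value at one particular event rate.

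**Working it through.** **Inputs.** From Power Analysis: n = 52 per arm, lidocaine rate 0.20, nominal alpha 0.05. Inferred: saline rate 0.02 (the measurement error read as an apparent-deficit rate) and a two-sided test.

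**Formulas.** Let b(x; n, p) be the binomial probability and R the set of tables (x lidocaine events, y saline events) that the test rejects.

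- Power = Σ over R of b(x; 52, 0.20) · b(y; 52, 0.02).
- Type I error at common rate p = Σ over R of b(x; 52, p) · b(y; 52, p). The size of the test is the maximum over p.
- Fisher: R holds the tables with two-sided p ≤ 0.05.
- Boschloo: R holds the tables with two-sided Fisher p ≤ c, where c is the largest cut-off with size ≤ 0.05. At 52/52, c = 0.0725.

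**Step 1: the plan's figures.** Two-sided Fisher gives power 0.8029 and type I error 0.00042 at a common rate of 2%. Both stated figures reproduce. The alternatives do not fit: one-sided 0.05 gives 0.897 and 0.0014, and one-sided 0.025 gives 0.803 and 0.0002.

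**Step 2: Boschloo at 52/52.** Because c exceeds 0.05, every table Fisher rejects is also rejected. At the assumed rates the gain comes from these added tables:

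| Lidocaine v saline events | b(x; 52, 0.20) | b(y; 52, 0.02) | Product |
|---|---|---|---|
| 5 v 0 | 0.0232 | 0.3497 | 0.0081 |
| 7 v 1 | 0.0746 | 0.3712 | 0.0277 |
| 9 v 2 | 0.1282 | 0.1932 | 0.0248 |
| 10 v 3 | 0.1378 | 0.0657 | 0.0091 |
| 12 v 4 | 0.1124 | 0.0164 | 0.0018 |
| 13 v 5 | 0.0864 | 0.0032 | 0.0003 |

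The products sum to 0.0718 with rounding, which agrees with 0.8746 − 0.8029 = 0.0717.

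**Step 3: type I error at 52/52.**

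| Common rate | Fisher | Boschloo |
|---|---|---|
| 2% | 0.0004 | 0.0027 |
| 5% | 0.008 | 0.022 |
| Maximum over all rates | 0.039 | 0.0495 |

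**Step 4: other evaluable numbers (20% v 2%).**

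| Lidocaine/saline | Fisher | Boschloo |
|---|---|---|
| 52/52 | 0.803 | 0.875 |
| 51/52 | 0.864 | 0.910 |
| 52/51 | 0.806 | 0.868 |
| 50/52 | 0.874 | 0.902 |
| 51/51 | 0.791 | 0.858 |
| 48/48 | 0.753 | 0.831 |

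Over the 25 splits with 0 to 4 lost per arm, the gain is 2.5 to 7.8 points. Fisher is below 80% in 9 of them and Boschloo in none. With equal losses, Boschloo holds 80% down to 45 per arm (0.807; at 44 it is 0.795). If randomisation were simple, average power over splits of 104 would be 0.854 v 0.877.

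**Step 5: sensitivity to the saline rate (52/52, lidocaine 20%).**

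| Saline rate | Fisher | Boschloo |
|---|---|---|
| 2% | 0.803 | 0.875 |
| 3% | 0.712 | 0.800 |
| 4% | 0.621 | 0.720 |
| 5% | 0.534 | 0.637 |

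The Procedure section lists eight tests per patient (four movements, both sides). If 2% applied to each, any one counted, and they were independent, the per-patient rate would be 1 − 0.98^8 = 14.9%.

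**Step 6: which variant.** Some software doubles the one-sided Boschloo p value (scipy does). At 52/52 this gives the same 0.8746. At 51/52 it gives 0.8636, no gain over Fisher. At 50/52 it gives 0.8518, below Fisher's 0.8744. The ordering statistic therefore has to be named.

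**The case against.** Nothing in the plan is wrong here. Fisher's test is valid, its power is correctly stated, and the analysis uses the test that sized the trial. Choosing a conditional over an unconditional exact test is a legitimate preference. That stands, and it is why this is an improvement and not an error.

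The size of the gain also depends on the split: at 51 lidocaine and 53 saline it is only 0.2 points (0.883 v 0.885). This stands as a caution, but 52/52 is the plan's own design, and there the gain is 7.2 points.

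The documents do not rank the two kinds of error. The Introduction describes the hazard of weakness, while Significance describes what is lost when local anaesthetic is omitted, so a false positive also has a cost. Boschloo raises type I error at a 2% common rate from 0.0004 to 0.0027. That is more than sixfold but far inside 0.05. The case for the change rests on power within the agreed alpha and does not need a ranking of errors.

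Finally, the missing rule for turning eight tests into one result matters more than the choice of test. With saline at 14.9% and lidocaine still at 20% (an assumption), power would be 6.6% v 9.3%. This is right, so the rule must come first.

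**Conclusion.** The point holds as a cheap improvement. At 52 evaluable patients per arm, 20% v 2% and two-sided 0.05, Boschloo's test ordered by the two-sided Fisher p value has power 0.875 against 0.803, with maximum type I error 0.0495 against 0.039. The saline rate and two-sidedness are inferred, but they match both of the plan's figures. Under one-sided 0.05 there would still be a gain (0.926 v 0.897). The gain shrinks for some uneven splits, and a higher saline rate would cost more power than the change of test recovers.

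The figure 0.0004 is correct as a number but is not a property of the design.

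The point covers only the between-arm comparison of motor-deficit proportions. It does not touch the other strength item under Primary outcome, individual change. Nor does it settle the conflict with the Data Analysis Plan, which says: "The primary outcome will be the proportion of participants with 50% or greater reduction in neck and arm pain". That must be resolved separately.

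**What to change.** Before unblinding:

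1. State how the 19.5% threshold turns the eight strength tests into one yes/no motor deficit per patient.
2. In Power Analysis and Statistical analysis, name Boschloo's exact unconditional test, two-sided 0.05, with the two-sided Fisher p value as its ordering statistic, for the between-arm comparison of that proportion. Confirm that the chosen software implements this variant and not the doubled one-sided p value.
3. Report the risk difference with a 95% confidence interval and name the interval method, since interval and test can disagree.
4. Restate power as about 87% if the per-patient rates are 20% v 2% with 52 evaluable per arm, and about 64% if the saline rate is 5%.
5. Replace the 0.0004 sentence with a statement that type I error is at most 0.05 for every common event rate. If Fisher's test is kept, say that 0.0004 is its type I error at a 2% common rate and that its maximum at 52/52 is 0.039.

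The cost is wording in two sections and a check of the software, with no extra patients or visits. The downsides are a test less familiar to clinical readers, a variant that must be specified, and actual type I error that is higher than Fisher's but within 0.05.

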### **Procedure**

All patients evaluated in the University of Utah Orthopaedic Center who will have a CESI with triamcinolone will be considered for participation in the study. Subjects will be consented for participation in the study and informed consent will be obtained. Each subject will be randomized into a group assignment in a 1:1 manner, #1 or #2, as outlined in the Methods section above. All documentation will be stored using a unique coded identifier to ensure compliance with HIPPA.

A Report Form will be used to record all pre- and post-procedure data (See Appendix)

In every participant in Control Cohort, Group 1 and Group 2, a pre-procedure NRS pain score, pain medication use, and presence of subjective or objective symptoms of UE weakness will be recorded. Bilateral handgrip, wrist extension, elbow flexion, and elbow extension strength (myotomes C5-T1) will be measured by a trained research assistant prior to the injection procedure using a handheld JAMAR® PLUS+ digital dynamometer (Sammons Preston, Bollingbrook, IL) for hand grip strength and a Lafayette Manual Muscle Testing System model 01163 (Lafayette Instrument Company, Lafayette, IN) for arm strength assessment. Three baseline strength measurements will be recorded for each strength test (20,21). Validation studies using similar protocols for upper extremity functional strength measurement show a high degree

of test-retest reliability with a narrow range of variability [22–26]. Additionally, light touch and pinprick sensory testing in the C5-T1 dermatomes will be performed with a tapered whisp of cotton and a disposable safety pin, respectively, in accordance with the methods described when performing an American Spinal Injury Association (ASIA) examination in accordance with the international standards for neurological classification of spinal cord injury (27).

Measurements will be taken prior to and 30 minutes following the injection procedure. Participants in Group #1 and Group #2 will also be queried with the Upper Extremity Functional Index (UEFI) before the injection procedure and again 1 day after the procedure (administered via telephone).

For Group 1 and Group 2, patients will be randomized to treatment group based on a random computer-generated schedule. Participants will be blinded to the group to which they are randomized. All standard procedures for CESIs will be followed as is standard practice including time out, skin prep, hemodynamic monitoring, image guidance, etc.

Per randomization, triamcinolone acetonide 80 mg (Kenalog) (E. R. Squibb & Sons Limited, Uxbridge UK) will be combined with 2mL Lidocaine 1% or 2 mL preservative free saline and will be injected during the CESI procedure. In all cases, the total injectate volume will be 4 mL. All injections will be image guided with fluoroscopy, as is the current standard practice. Fluoroscopy time will be recorded.

The participant will be discharged from the clinic with written discharge instructions (current standard practice).

Participants will be telephoned and emailed by clinic personnel 1 day after the CESI to assess for subjective weakness in the hands or arms as well as any other adverse reactions. As above, the UEFI will be administered at this time.

Participants will only be recruited for this study for a single CESI. Those who require repeat injections will not be recruited a second or third time.

